#### Antibiotic Use Follow-up Days:

- Assess for capacity to consent
- Surgical procedures
- Bedside procedures, interventions
- Diagnostic imaging
- Standard of care lab values (e.g. CBC, bacterial cultures, PCT, etc.)
- Antibiotic information

### 11.7 Record retention

All study data will be retained by Isomark and the study site for a minimum of seven years after completion of the study. After seven years, paper documents will be destroyed. Electronic data will be deleted.

### 11.8 Investigator compliance

The investigator study team, i.e. study site and Isomark LLC, will conduct the trial in compliance with the protocol approved by the IRB. Changes to the protocol will require written IRB approval prior to implementation, except when the modification is needed to eliminate an immediate hazard(s) to subjects.

### 11.9 Subject cost and payment

#### **Cost**

Subjects will not incur costs due to their participation in this study. Laboratory testing done as part of the study will be paid by the sponsor, Isomark, LLC.

#### **Payment**

Subjects will not be paid for participation in this study.

### 11.10 Quality Control

Study personnel will complete sample collection and sample analysis records to ensure proper sample collection analysis and data reporting for each subject enrolled.

- When a new subject is enrolled in the study, the study team member will label and complete the sample collection records with the subject's study number.
- The study team member will notify Isomark personnel by email that a new subject is enrolled.
- At each subsequent breath collection time, a study team member will label the breath sampling equipment with the subject study number, site number, date and time when each sample was collected. The study team member will complete and initial the relative collection records within the Case Report Form (CRF). If the sample is

obtained late, then the reason will be documented, e.g. subject in MRI. Each breath sample will be collected as close as possible and not exceeding one hour prior to or after the designated time for the sample collection.

- At each blood collection time, a study team member will label blood sampling equipment with collection date and time. Isomark will provide pre-printed labels with each subject's study number. The study team member will complete and initial the blood sample collection record, accounting for the time of collection, time of spinning, and time of freezing. The total time between collection and freezing cannot exceed four hours. If a sample is not collected on a given day, it will be considered missing data.
- A study team member will collect a breath sample every four hours and a blood sample every 24 hours for the duration that the subject is in the ICU or IMC and initial the sample collection records at each time-point.
- Collected breath samples and the original copies of the corresponding sample collection records will be shipped to Isomark within 48 hours of final collection from a subject via a shipping service, such as UPS or FedEx, to Isomark's breath analysis lab. If multiple subjects are enrolled, then shipments will be made once per week.
- Blood samples and the original copies of the corresponding blood sample collection records will be placed in an Isomark-provided container and shipped to Isomark's contracted reference lab via an Isomark-approved carrier. The blood samples are processed by the reference lab and the results are sent to the sites, and will need to be entered into the EDC by the site staff. After the results have been successfully received, the lab will dispose of any remaining blood samples.
- Each time breath samples are received, Isomark personnel will check the samples for complete label information and compare the samples to the EDC, noting any anomaly. Isomark personnel will then update the corresponding sample check-in record with sample arrival, inspection, and condition information, dating and initialing where instructed.
- At the beginning of each day on which samples are analyzed, the sample analysis technician will ensure the Canary is within calibration specifications by analyzing a standard sample of known isotopic composition and initial the sample analysis record.
- Breath samples are to be analyzed within 21 days of the time of collection. Isomark personnel will note the time and date of sample analysis on the sample analysis record and initial.
- Data will be recorded on the sample analysis record and initialed by the technician.
- After breath sample analysis is complete, the technician will ensure the remaining breath is exhausted (by expelling all remaining sample from the sample bag) or destroyed (by disposal as biomedical waste in the case of plasma samples) and will initial the sample analysis record.
- After breath analysis is complete, Isomark personnel will enter the results into the EDC.

### 11.11 Funding source

This study is sponsored by Isomark, LLC.

### 12.0 FDA Investigational Device Exemption (IDE) information

This study will be conducted in accordance with the regulations outlined in 21CFR812.

- a. As per §812.2(c)(3), the study involves a diagnostic system (see below) which is itself non-invasive, does not require invasive sampling, does not introduce energy into the subject, and requires the confirmation of the presence or lack of SIRS via standard physical examination and laboratory testing (white blood count and differential). As such, this study/this device is deemed IDE exempt.
  - i. The physical devices used in this study consist of:
    - commercially-available ventilator tubing and adaptors
    - gas-tight bags
    - Isomark isotopic carbon ratiometer for performing the carbon isotope ratio diagnostic measurement
    - Pee Dee Belemnite as a reference gas sample.

Each of these is used in accordance with its design intent, is legally owned by the sponsor, Isomark LLC, and does not require any additional labeling or special shipping controls. For purposes of complying with §812.5, computers with which applicable analysis software is used will be labeled 'Caution: Investigational Device. Limited by Federal Regulations to Investigational Use'.

- b. This study is being reviewed by Western IRB (WIRB) or the site specific local IRB.
- c. For this study, the PI will maintain records of this study as per § 812.140.

## 1. Abbreviations

AE	Adverse Event
BDV	Breath Delta Value
CDM	Clinical Data Management

## 2. Study Summary

The Isomark Canary™ is a device designed to measure the breath delta value (BDV) in exhaled breath samples obtained from a patient. The BDV is a ratio of the two primary naturally occurring isotopic forms of carbon dioxide,  $^{13}\text{CO}_2/^{12}\text{CO}_2$ . Changes in the BDV can indicate the onset of infection due to the phenomenon known as the acute phase response, which occurs early in the infection process, even before a patient shows typical symptoms of an infection. Breath samples are collected in a disposable, single-use bag. The study is designed to collect data that can demonstrate the effectiveness of the BDV as an indicator of infection as compared to current methods, such as vital signs.

This is a prospective study using subjects who are not suspected of infection at the time of enrollment and comparing the Canary's BDV marker to standard infection monitoring methods.

## 3. Roles and Responsibilities

The Isomark team is involved in research (protocol) design and breath sample analysis.

## 4. Data Source

The purpose of this Statistical Analysis Plan (SAP) is to outline the processes in which the statistical considerations were made for this protocol. It will serve as documentation for the clinical data management procedures that will be followed for Isomark's CANARY01 trial.

Data will be collected from clinical sites on adult subjects that have been identified as critically ill who are at risk for developing an infection. Subjects will be enrolled based on the following criteria:

### Inclusion criteria

1. Age 18 years or older
2. Critically ill patient admitted to the Intensive Care Unit (ICU)
3. High risk of infection, per Investigator discretion
4. Enrolled within 48 hours of ICU admittance (see Enrolled definition in section 6.1)
5. Expected duration of hospital stay at least 120 hours (five days) from time of study enrollment
6. Subject/LAR speaks a language of which the IRB has approved a consent form

### Exclusion criteria

1. Confirmed infection at time of enrollment
2. Known use of non-prophylactic antibiotics, antimicrobials and/or antifungals for more than 24 hours prior to ICU admission
3. Currently active cancer, defined as receiving treatment or intend to receive treatment within hospital stay for cancer (including but not limited to: radiation, chemotherapy, systemic orals, etc)
4. If not intubated, unable to cooperate with providing a breath sample
5. Expected death within 24 hours of enrollment or lack of commitment to aggressive treatment by family/medical team (e.g., likely to withdraw life support measures within 24 hrs of screening)
6. Female who is pregnant or lactating (negative serum or urine pregnancy test results within 48 hours of enrollment or to be performed during screening)
7. Prisoner
8. Ethnic/Racial/Covariate category has completed enrollment
9. Known participation in an investigational and interventional research study within 30 days prior to enrollment, not approved in advance by sponsor (note: to be eligible, any interventional treatment must have ended at least 30 days ago)
10. Individuals who are directly affiliated with sponsor or study staff, or their immediate families. Immediate family is defined as spouse, domestic partner, parent, child, or sibling whether legally adopted or biological.
11. Any patient that is deemed unfit for study participation, per the Investigator's discretion

Data collected includes:

- Open enrollment of subjects, population defined by inclusion/exclusion criteria
- Subject breath sample taken at enrollment and every 4 hours for the duration of the subject's ICU stay
- SIRS/MEWS and vitals data
- Subject records monitored/collected daily
- Daily blood samples collected for the duration of the subject's ICU stay and stored for

subsequent analysis of CRP and PCT

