#### 3.1.2 Exclusion criteria

- 1) known or suspected infection at time of enrollment
- 2) known use of systemic antibiotic, antimicrobial and/or antifungal therapy within the seven (7) days prior to hospital admission
- 3) currently active cancer, defined as receiving treatment or intend to receive treatment within hospital stay for cancer (including but not limited to: radiation, chemotherapy, systemic orals, etc)
- 4) if not intubated, unable to cooperate with providing a breath sample

- 5) expected death within 24 hours of enrollment or lack of commitment to aggressive treatment by family/medical team (e.g., likely to withdraw life support measures within 24 hrs of screening)
- 6) female who is pregnant or lactating (negative serum or urine pregnancy test results within 48 hours of enrollment or to be performed during screening)
- 7) prisoner
- 8) known participation in an investigational and interventional research study within 30 days prior to enrollment, not approved in advance by sponsor (note: to be eligible, any interventional treatment must have ended at least 30 days ago)
- 9) Individuals who are directly affiliated with sponsor or study staff, or their immediate families. Immediate family is defined as spouse, domestic partner, parent, child, or sibling whether legally adopted or biological.
- 10) Any patient that is deemed unfit for study participation, per the Investigator's discretion.

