For critically ill patients admitted to an ICU, the mean overall nosocomial infection rate is 6 to 18% (29, 30, 40). The incidence rate of infection could be greater for all surgical ICU patients. The infection rate in the previous proof-of-concept study was 50% using the same population and inclusion/exclusion criteria; this assumption of equal proportions of prospectively enrolled infected and uninfected subjects will be used in the sample size calculations which follow. Data collected to date indicate that a sustained change in BDV of 1.0‰ or more correlates with the presence of infection when the subject is used as his-her control. The average intra subject standard deviation (SD) across time points in critically ill adult subjects previously studied was 0.95‰, regardless of the underlying medical conditions. The inter subject SD is expected to be 1.0‰ at most. Using the BDV measurements during the breath sample monitoring period (breath sample assessments every 4 hours), the expected overall SD of the mean BDV measurements (across time points) is less than 1.0‰.

BDV sensitivity and specificity will be evaluated relative to PCT sensitivity and specificity according to non-inferiority hypothesis tests where a greater than 10% BDV disadvantage is to be ruled for both sensitivity and specificity relative to a less than 10% BDV disadvantage. The BDV sensitivity and specificity estimates will then be used to determine the positive predictive value (PPV) and negative predictive value (NPV) once the prevalence is known; prevalence surrogates can be used to apply the observed sensitivity and specificity to various ICU and CCU settings.

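### The SAP and the protocol give conflicting eligibility criteria, the per-protocol set has no membership rule, and the SAP's 50% infection rate rests on criteria that are not settled

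*SAP*

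**What the plan says.** SAP section 4 presents its inclusion and exclusion lists as the basis for enrolment. They differ from protocol sections 3.1.1 and 3.1.2 in four places.

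- **Infection at entry.** SAP: "Confirmed infection at time of enrollment". Protocol: "known or suspected infection at time of enrollment"; the infection definition in protocol section 6.1 repeats that suspicion alone makes a patient ineligible.
- **Prior antibiotics.** SAP: "Known use of non-prophylactic antibiotics, antimicrobials and/or antifungals for more than 24 hours prior to ICU admission". Protocol: "known use of systemic antibiotic, antimicrobial and/or antifungal therapy within the seven (7) days prior to hospital admission". Protocol section 6.1 (Antibiotic Use) permits routine perioperative antibiotics and refers to continuous systemic therapy when it defines an infection failure.
- **Risk.** The SAP includes only patients at "High risk of infection, per Investigator discretion". Protocol section 3.1.1 has no such criterion.
- **Enrolment cap.** The SAP excludes a patient when "Ethnic/Racial/Covariate category has completed enrollment". Protocol section 3.1.2 has no such rule.

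The SAP list also disagrees with the SAP's own Study Summary (section 2), which describes subjects in whom infection is not suspected at enrolment. SAP section 10 records no deviation from plan.

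On the event rate, SAP section 5 states: "The infection rate in the previous proof-of-concept study was 50% using the same population and inclusion/exclusion criteria". It carries that proportion into the sample size. The same paragraph cites a 6 to 18% nosocomial infection rate for critically ill ICU patients. Protocol section 7.1 cites 6 to 18% for trauma ICU patients and sizes the study on 5%, with 10% as the alternative.

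**The concern.** Three parts of the analysis depend on who is eligible.

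1. **The analysed set.** SAP section 6 names a per-protocol analysis but gives no membership rule. Protocol Table 1 (section 5.12) replaces subjects found not to meet the criteria and leaves them out of the primary analysis. With two lists in force, the same subject can be in or out.
2. **The baseline.** SAP section 5 calls BDV positive when it moves more than 1‰ from baseline within 24 hours, and refers to a pre-infection mean. SAP section 6 makes each subject its own control. A subject already infected, but not yet confirmed, when the first breath sample is taken may have no uninfected baseline. That weakens any claim that BDV leads the diagnosis.
3. **The event rate.** The SAP's 50% is justified by unchanged population and criteria. If the criteria are in dispute, so is that justification, and the number to enrol depends on it.

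**Working it through.** **Which subjects change status.** Read side by side, neither list contains the other (each case assumes all other criteria are met):

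| Subject | SAP list | Protocol list |
|---|---|---|
| Suspected, unconfirmed infection at enrolment | eligible | excluded |
| Therapeutic systemic antibiotics for under 24 hours, within the week before hospital admission | eligible | excluded |
| Therapeutic antibiotics for more than 24 hours, all between hospital and ICU admission | excluded | not excluded by the antibiotic rule, though suspected infection may exclude |
| Not judged at high risk of infection | excluded | eligible |
| Covariate category already full | excluded | eligible |

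The SAP list is looser in some rows and tighter in others. The net effect on the infection rate therefore cannot be derived from the wording.

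**The plans' own power figures.**

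*SAP Table 1.* Inputs: expected difference Δ = 0.10, discordant proportion η = 0.40, margin −0.10, one-sided 2.5%, n = 97 pairs. The Wald approximation for paired proportions is

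power = Φ[(Δ + 0.10)√n / √(η − Δ²) − 1.96]
= Φ[0.20 × 9.849 / √0.39 − 1.96] = Φ(3.154 − 1.96) = Φ(1.194) = 88.4%.

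Simulation with 200,000 runs gives 88.3%. The SAP states 89% for sensitivity and 87% for specificity (Table 2, same Δ and η). With 1,000 simulations in each SAP table, these agree.

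*Protocol section 7.1.* Inputs: 5 infected against 95 non-infected, difference 2.0‰, SD 1.5‰, two-sided 5%. The noncentrality is 2.0 / (1.5 × √(1/5 + 1/95)) = 2.91, and the power is 82% (stated: at least 80%). With 10 against 90 it is 98%, as stated.

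The arithmetic in both documents holds. What differs is the infection rate and the population.

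**Enrolment implied by 97 infection events.** At infection rate p, the total needed is the larger of 97/p and 97/(1 − p), because 97 non-infected subjects are also required.

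| Rate p | Source | Total for 97 infected |
|---|---|---|
| 50% | SAP section 5 | 97/0.50 = 194 |
| 18% | upper end cited in SAP section 5 | 97/0.18 = 539 |
| 10% | protocol alternative | 97/0.10 = 970 |
| 6% | lower end cited in SAP section 5 | 97/0.06 = 1,617 |
| 5% | protocol assumption | 97/0.05 = 1,940 |

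**If enrolment stopped at 194** (an assumption; the SAP gives the two event counts, not this total), the sensitivity comparison would have:

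- at 18%: 194 × 0.18 ≈ 35 infected, power about 47%;
- at 10%: about 19 infected, power about 29%;
- at 6%: about 12 infected, power about 17 to 20%, depending on the method.

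Both co-primary endpoints must succeed, so low power on sensitivity limits the whole study.

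**The case against.** The strongest reply is that the SAP was written for another protocol version. It speaks of a modified study design (section 7), reports an extubation comparison in subjects already studied (section 6), and has breath samples analysed on site (section 11), where protocol section 5.8 ships them to the sponsor. This is plausible and would explain the conflict. It would not remove it: SAP section 10 records no deviation, and the SAP disagrees with its own summary.

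Four stronger readings are tempting and not supported.

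- **That sites enrolled a population other than the one the SAP describes.** Protocol section 11.8 requires conduct under the IRB-approved protocol, which favours the protocol list, but nothing shows which list sites used.
- **That the per-protocol set is tied to the SAP list.** It is undefined, which is a different fault.
- **That 539 to 1,617 measures the effect of the eligibility mismatch.** The 50% and the 6 to 18% stand in one SAP paragraph, so the tension would remain if the lists matched. The rates may also count different things: the protocol counts confirmed nosocomial infection, the SAP rate is not defined, and the SAP hypotheses concern severe sepsis and septic shock. Both documents add that surgical ICU rates could be higher. A lower rate raises the enrolment needed; it does not reduce power once 97 events are reached. Nor does the SAP state a total of 100, so setting 50 infected against the protocol's 5 would mix two designs.
- **That infections present at entry would be counted as detected.** Suspected is not the same as infected, the SAP still excludes confirmed cases, its co-primary hypotheses concern progression, and the adjudicators are blinded to BDV (protocol section 10.1).

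The antibiotic gap is also narrower than the exclusion lists alone suggest, because protocol section 6.1 permits perioperative use. The difference in window and reference point remains.

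**Conclusion.** The conflict between the lists is established from the text on all four points, together with the SAP's disagreement with its own summary. It goes beyond wording, because eligibility decides who is analysed under protocol Table 1 and the SAP supplies no per-protocol rule of its own. The baseline problem is a possibility for subjects with suspected infection, and its frequency cannot be estimated from the documents. SAP section 6 has the adjudication committee date severe sepsis and septic shock; it does not clearly require a date for infection onset, so such subjects might not be identifiable from adjudication alone.

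The event-rate issue is related but separate. The 50% is not supported for the protocol population, and the enrolment for 97 infection events runs from 194 at that rate to about 539 at 18% and 1,617 at 6%. These totals assume that the cited rates apply to the events being counted and that each infected subject contributes one pair. The share due to eligibility is unknown. This should be settled before database lock.

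**What to change.** 1. Reconcile SAP section 4 with protocol sections 3.1 and 6.1 and with SAP section 2, so that one list stands in both documents. Which clinical criteria are right is for the sponsor and investigators. State which list was in force for subjects already enrolled, and record any change in SAP section 10.
2. Define the per-protocol set explicitly by the reconciled list and protocol Table 1.
3. Re-justify or restate the 50% rate for that population: identify the earlier study's criteria, say what was counted as an infection, and give the enrolment implied across the cited range.
4. Add a sensitivity analysis that excludes subjects whose adjudicated or clinically documented infection onset falls at or before the first breath sample. Have the adjudication form record infection onset as well as severe sepsis and septic shock onset.

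Cost: SAP wording, one added field on the adjudication form, and one extra analysis. The stated sample-size assumption may also become less favourable.

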## 5. Analysis Objectives

The overall objective of the analysis is to demonstrate that the BDV is a leading marker for infection diagnosis in critically ill subjects. Key questions to be answered are 1) Evaluate the BDV as a marker of infections in critically ill subjects at risk of progressing to severe sepsis and septic shock; 2) To measure variation of BDV with time in critically ill ICU patients progressing to severe sepsis and septic shock among those who agree to participate as research subjects; 3) To determine the magnitude of change of BDV in subjects who subsequently progress to severe sepsis and septic shock; 4) To define variation of BDV in critically ill ICU subjects who do not progress to severe sepsis and septic shock.

The BDV will be analyzed to determine the range of exhaled  $^{13}\text{CO}_2/^{12}\text{CO}_2$  BDV in adult subjects. The  $^{13}\text{CO}_2/^{12}\text{CO}_2$  BDV will be compared with current clinical standard scores, physiologic measurements and biomarkers (e.g. vital signs, WBC, CRP, PCT), and any interventions -- such as antibiotic administration -- will be noted for the purpose of assisting in understanding variation of BDV. For the purpose of defining a positive BDV for the presence of an infection, a positive BDV is defined as a change of greater than 1‰ within a 24-hour period above or below the baseline value. The 1‰ threshold for change in the BDV within 24 hours is based on the variability of approximately 0.5‰ seen in subjects with stable nutrition who do not develop infections. Thus, a change of 2 standard deviations away from the pre-infection mean will be examined as part of sensitivity among those with progression to severe sepsis and septic shock and positive predictive value for progression to severe sepsis and septic shock.

For critically ill patients admitted to an ICU, the mean overall nosocomial infection rate is 6 to 18% (29, 30, 40). The incidence rate of infection could be greater for all surgical ICU patients. The infection rate in the previous proof-of-concept study was 50% using the same population and inclusion/exclusion criteria; this assumption of equal proportions of prospectively enrolled infected and uninfected subjects will be used in the sample size calculations which follow. Data collected to date indicate that a sustained change in BDV of 1.0‰ or more correlates with the presence of infection when the subject is used as his-her control. The average intra subject standard deviation (SD) across time points in critically ill adult subjects previously studied was 0.95‰, regardless of the underlying medical conditions. The inter subject SD is expected to be 1.0‰ at most. Using the BDV measurements during the breath sample monitoring period (breath sample assessments every 4 hours), the expected overall SD of the mean BDV measurements (across time points) is less than 1.0‰.

BDV sensitivity and specificity will be evaluated relative to PCT sensitivity and specificity according to non-inferiority hypothesis tests where a greater than 10% BDV disadvantage is to be ruled for both sensitivity and specificity relative to a less than 10% BDV disadvantage. The BDV sensitivity and specificity estimates will then be used to determine the positive predictive value (PPV) and negative predictive value (NPV) once the prevalence is known; prevalence surrogates can be used to apply the observed sensitivity and specificity to various ICU and CCU settings.

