## **6. Analysis Sets/Populations/Subgroups**

The first task is to demonstrate that there is a positive signal associated with the Canary test using the subject as their own control.

A per protocol analysis will be performed following EAC event reconciliation and subsequent database lock. The EAC will determine diagnostic truth by documenting severe sepsis or septic shock events as well as the onset and resolution dates.

Infection documentation will be reviewed by the EAC committee based on best clinical practices, using four categories:

- No suspicion of infection
- Inconclusive evidence of infection
- High suspicion of infection
- Overt infection

For sensitivity and specificity, non-inferiority testing will be performed to rule out a -10% disadvantage according to a one-sided 97.5% lower confidence limit for the BDV – PCT

difference; exact McNemar paired comparison tests will be performed to test BDV non-inferiority relative to PCT. Both endpoints must achieve statistical significance in order to achieve study success.

PPV and NPV will be computed as observed and for a range of possible infection prevalence (10%, 20%, 30%, and 40%). Results will be analyzed in the same manner as sensitivity and specificity.

BDV variations will be assessed using a two-sample t-test to compare the averaged (across time points) BDV between subjects who are diagnosed with a severe sepsis and sepsis shock vs. no severe sepsis or sepsis shock. Also a linear mixed effects model with subject specific random effects will be used to compare BDV measurements between the two diagnostic groups. This model will be also used to estimate the intra- and inter-subject variability of the BDV measurements. A paired t-test will be used to compare the BDV measurements prior to and after a diagnosis of infection or sepsis.

The definition of a positive BDV will be based on a 72-hour window without advance knowledge of the diagnosis. In the absence of clinical details supporting PCT operating characteristics (sensitivity, specificity), two PCT thresholds (0.5 and 2.0) will be evaluated but the 0.5 threshold is deemed to be primary for BDV comparison.

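### The SAP names two unreconciled references for BDV change; the one tied to sensitivity and PPV needs an infection date and does not exist for never-infected subjects

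*SAP*

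**What the plan says.** SAP section 5 (Analysis Objectives) first gives a rule that can be applied to any subject: "a positive BDV is defined as a change of greater than 1‰ within a 24-hour period above or below the baseline value". It justifies the 1‰ cut-off as "based on the variability of approximately 0.5‰ seen in subjects with stable nutrition who do not develop infections". The next sentence, introduced as a consequence, says that "a change of 2 standard deviations away from the pre-infection mean will be examined as part of sensitivity among those with progression". The same sentence attaches this quantity to a second measure: "positive predictive value for progression to severe sepsis and septic shock". Neither the baseline value nor the pre-infection mean is defined by number or timing of samples.

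SAP section 6 adds: "The definition of a positive BDV will be based on a 72-hour window without advance knowledge of the diagnosis". On the reference standard it says: "The EAC will determine diagnostic truth by documenting severe sepsis or septic shock events as well as the onset and resolution dates". Sensitivity and specificity against PCT are co-primary: "Both endpoints must achieve statistical significance in order to achieve study success". On predictive values, section 5 says: "The BDV sensitivity and specificity estimates will then be used to determine the positive predictive value (PPV) and negative predictive value (NPV"), once a prevalence is known.

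**The concern.** The reference is part of the index test. A mean that stops at infection onset can be formed only after someone has decided that there was an infection and dated it. A subject who never becomes infected has no such mean, and the SAP does not say what takes its place. Those subjects all count towards specificity, and any positives among them are false positives in PPV.

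An analyst who follows section 5 to the letter would score progressors against one reference and never-infected subjects against another. A mean of many samples is less noisy than one sample, so the two groups could have different chances of crossing 1‰ even if BDV carried no information. The per-protocol analysis comes after the adjudication committee has reconciled events. If the reference stays open, it can therefore be chosen when the diagnoses are already known. Both co-primary endpoints depend on it, and so do PPV and NPV.

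**Working it through.** **Step 1. The plan's own figure.** 2 × 0.5‰ = 1.0‰. At an SD of 0.5‰ the two sentences share a cut-off and differ only in the reference. SAP section 5 also gives an intra-subject SD of 0.95‰. On that figure 1‰ is 1/0.95 = 1.05 SD, and 2 SD is 1.9‰. The cut-offs agree only at 0.5‰.

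**Step 2. Who has each reference.**

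| Subject | Counts towards | Baseline value | Pre-infection mean |
|---|---|---|---|
| Progressor to severe sepsis or septic shock | Sensitivity | Yes | Only once infection is dated |
| Infected, no progression | Specificity; PPV false positives | Yes | Only once infection is dated |
| Never infected | Specificity; PPV false positives | Yes | None |

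Only the baseline value exists for every subject, and only it can be formed without the diagnosis, as section 6 requires. The onset dates that section 6 assigns to the committee are, as written, those of severe sepsis or septic shock events. Infection itself is graded in four categories.

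**Step 3. Does the reference matter? One reading, no true change.** Assume independent normal readings and a reference that is the mean of *k* earlier readings. The difference has variance SD²(1 + 1/k), so

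P(positive) = 2[1 − Φ(1 / (SD√(1 + 1/k)))].

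For SD 0.5‰ and k = 1: 0.5 × √2 = 0.707, 1/0.707 = 1.414, P = 15.7%. For k = 30: 0.5 × √(31/30) = 0.508, 1/0.508 = 1.967, P = 4.9%.

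| SD | k = 1 | k = 6 | k = 18 | k = 30 |
|---|---|---|---|---|
| 0.5‰ | 15.7% | 6.4% | 5.2% | 4.9% |
| 0.95‰ | 45.7% | 33.0% | 30.6% | 30.0% |

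**Step 4. Over a window, no true change.** Simulated subjects, positive if any reading differs from the reference by more than 1‰. At one sample every 4 hours, 24 h is 6 readings and 72 h is 18. Readings are independent here.

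| SD, window | k = 1 | k = 6 | k = 18 | k = 30 |
|---|---|---|---|---|
| 0.5‰, any of 18 | 81.4% | 66.9% | 61.1% | 59.3% |
| 0.5‰, any of 6 | 52.5% | 32.2% | 27.1% | 26.1% |
| 0.95‰, any of 6 | 94.6% | 90.3% | 88.8% | 88.3% |
| 0.95‰, any of 18 | 99.9% | 99.9% | 99.8% | 99.8% |

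Correlation between successive readings changes the picture:

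- SD 0.5‰, any of 18, first reading versus 30-reading mean: about 75% versus 56% at lag-1 correlation 0.5, and about 60% versus 43% at 0.8.
- SD 0.5‰, any of 6, correlation 0.8, one reading taken immediately before the window versus 30-reading mean: 17.5% versus 18.1%, no material gap. A single reading taken well before the window reopens the gap.
- SD 0.95‰, any of 18: about 97% or more under either reference at correlations from 0 to 0.8.

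**Step 5. Sample size.** SAP Table 1 uses the expected difference (0.10), the discordant proportion (0.40), the limit (−0.10) and 97 pairs. Φ(0.20/√((0.40 − 0.01)/97) − 1.96) = Φ(3.154 − 1.96) = 88.4%, against 89% printed. The reference is not an input, so no sample-size figure changes.

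**The case against.** The strongest reply is that there is only one rule. Section 5 states a general definition of a positive BDV. The 2 SD sentence follows as its explanation, and 2 × 0.5‰ = 1‰ fits that. Confirmed infection at enrolment is an exclusion in SAP section 4, and the subject is meant to serve as his or her own control. Pre-infection mean may therefore be loose wording for the subject's own baseline. The blinding statement in section 6 supports this reading, and PPV and NPV are said to follow from the sensitivity and specificity estimates.

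Much of this stands. A reader might infer that the SAP plans different tests for sensitivity and specificity. It does not say so: nothing gives specificity a separate rule. The split is not exact either, because infected non-progressors count towards specificity and do have a pre-infection period.

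What the reply does not remove is the sentence itself. A shared cut-off is not a shared reference, and the sentence says what will be examined for sensitivity and PPV. A programmer could follow either term. The blinding statement shows what was intended, but it leaves the conflict in the text.

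The second reply concerns size. Any-of-18 is only one reading of the 72-hour window: section 5 speaks of change within 24 hours and elsewhere of sustained change. The one-reading baseline and the 30-reading mean are both assumptions. This reply is right, and it limits what can be claimed.

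**Conclusion.** The point holds as an unresolved conflict over the reference. One of the two named references needs an infection date, is undefined for never-infected subjects and cannot meet the SAP's own requirement that positivity be set without knowing the diagnosis. This goes beyond missing detail, because the sentence fails if it is followed.

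Neither the size nor the direction of any bias can be fixed from the documents. At SD 0.5‰ with any of 18 independent readings, the no-signal positive rates are 81% (one reading) and 59% (30-reading mean), and 67% and 59% if baseline is 6 readings. They are about equal for any of 6 readings at correlation 0.8 with an adjacent reading, and over 72 h at SD 0.95‰. All these figures assume stationary normal readings.

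A reader might take the widest gap, 59.3 − 81.4 = −22 points in sensitivity plus specificity minus 1, and call it about twice the 10-point margin. The documents do not support that. It is one point in a wide range, it maps infected and uninfected onto the two endpoints only approximately, and the margin applies to a paired BDV − PCT difference tested separately for each endpoint. In that setting the shift works against BDV; it reverses if baseline is the less noisy reference.

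**What to change.** In SAP section 5, remove the pre-infection mean from the sentence on sensitivity and PPV. Name one reference that needs no diagnosis date, for example a fixed early set of the subject's own valid samples or a fixed trailing set before each scored window. State how many samples it needs. Apply the same reference, cut-off and window to progressors and non-progressors for sensitivity, specificity, PPV and NPV, and repeat the rule in section 6 beside the 72-hour statement. Fix it before anyone choosing the rule sees the adjudicated dates. Change from the pre-infection mean can stay as a description of the size of change in progressors (SAP objective 3).

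The cost is wording and programming, with no new data and no change in sample size. There are two drawbacks. No score is available while the reference is being formed, and a trailing reference could absorb a gradual decline in BDV. The second should be weighed when choosing between an early and a trailing set.
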